7.1 Sponsor-Investigator Reporting Requirements

7.1.1 Reporting to the Human Research Protection Office (HRPO) at Washington University

Reporting will be conducted in accordance with Washington University IRB Policies.

Pre-approval of all protocol exceptions must be obtained prior to implementing the change. The PI is required to promptly notify the IRB of the following events:

7.1.2 Reporting to the Quality Assurance and Safety Monitoring Committee (QASMC) at Washington University

The Sponsor investigator is required to notify the QASMC of any unanticipated problems involving risks to participants or others occurring at WU or any BJH or SLCH institution that has been reported to and acknowledged by HRPO. (Unanticipated problems reported to HRPO and withdrawn during the review process need not be reported to QASMC.)

QASMC must be notified within **10 days** of receipt of IRB acknowledgment via email to [contact]. Submission to QASMC must include the myIRB form and any supporting documentation sent with the form.

7.1.3 Reporting to the FDA

The conduct of the study will comply with all FDA safety reporting requirements. **PLEASE NOTE THAT REPORTING REQUIREMENTS FOR THE FDA DIFFER FROM REPORTING REQUIREMENTS FOR HRPO/QASMC.** It is the responsibility of the Washington University principal investigator to report to the FDA as follows:

- Report any unexpected fatal or life-threatening suspected adverse reaction (refer to Appendix G for definitions) no later than **7 calendar days** after initial receipt of the information.
- Report a suspected adverse reaction that is both serious and unexpected (SUSAR, refer to Appendix G) no later than **15 calendar days** it is determined that the information qualifies for reporting. Report an adverse event (Appendix G) as a suspected adverse reaction only if there is evidence to suggest a causal relationship between the drug and the adverse event, such as:
 - A single occurrence of an event that is uncommon and known to be strongly associated with drug exposure
 - One or more occurrences of an event that is not commonly associated with drug exposure but is otherwise uncommon in the population exposed to the drug

- An aggregate analysis of specific events observed in a clinical trial that indicates those events occur more frequently in the drug treatment group than in a concurrent or historical control group
- Report any findings from epidemiological studies, pooled analysis of multiple studies, or clinical studies that suggest a significant risk in humans exposed to the drug no later than 15 calendar days after it is determined that the information qualifies for reporting.
- Report any findings from animal or in vitro testing that suggest significant risk in humans exposed to the drug no later than 15 calendar days after it is determined that the information qualifies for reporting.
- Report any clinically important increase in the rate of a serious suspected adverse reaction of that listed in the protocol or IB within 15 calendar days after it is determined that the information qualifies for reporting.

Submit each report as an IND safety report in a narrative format or on FDA Form 3500A or in an electronic format that FDA can process, review, and archive. Study teams must notify the Siteman Cancer Center Protocol Development team of each potentially reportable event within 1 business day after initial receipt of the information, and must bring the signed 1571 and FDA Form 3500A to the Siteman Cancer Center Protocol Development team no later than 1 business day prior to the due date for reporting to the FDA.

Each notification to FDA must bear prominent identification of its contents (“IND Safety Report”) and must be transmitted to the review division in the Center for Drug Evaluation and Research (CDER) or in the Center for Biologics Evaluation and Research (CBER) that has responsibility for review of the IND. Relevant follow-up information to an IND safety report must be submitted as soon as the information is available and must be identified as such (“Follow-up IND Safety Report”).

7.1.4 Reporting to GSK

In addition to events described in Section 7.4 as reportable, all events of possible drug-induced liver injury with hyperbilirubinemia defined as ALT \geq 3x ULN **and** bilirubin \geq 2x ULN (>35% direct) (or ALT \geq 3x ULN and INR > 1.5, if the INR is measured) termed ‘Hy’s Law’ events (INR measurement is not required and the threshold value stated will not apply to subjects receiving anticoagulants) should be reported.

Any pregnancy that occurs during study participation must be reported. To ensure subject safety, each pregnancy must be reported within 2 weeks of learning of its occurrence. The pregnancy must be followed up to determine outcome (including premature termination) and status of mother and child. Pregnancy complications and elective terminations for medical reasons must be reported as an AE or SAE. Spontaneous abortions must be reported as an SAE.

Any SAE occurring in association with a pregnancy, brought to the investigator’s attention after the subject has completed the study and considered by the investigator as possibly related to the study treatment, must be promptly reported to GSK.

Safety information should be sent via email notification **within 24 hours of awareness** for all SAEs and AEs of Interest, and within 60 days for any other reportable non-serious events to [contact] (backup [contact]).

7.1.4.1 Adverse Events of Special Interest:

The frequency of all (both serious and non-serious) of the following Adverse Events of Special Interest will be assessed and included in the final report:

- Serious Hypersensitivity or Infusion Reactions
- Serious infections, including herpes zoster and opportunistic infections
- Malignancy
- Suicidal thought, intent or behaviour

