5.7 Management of Adverse Clinical Events and Dose Modification Guidelines

Belimumab is generally a well-tolerated agent. Most common adverse reactions are: nausea, diarrhea, pyrexia, nasopharyngitis, bronchitis, insomnia, depression, migraine. Management guidelines for some potential events are outlined below. Further details are available in the Investigator's Brochure. All serious AEs, including AEs of Special Interest, i.e., serious hypersensitivity or infusion reactions; serious infections, including herpes zoster and opportunistic infections; malignancy; and/or Suicidal thought, intent or behaviour must be reported to GSK within 24 hours of awareness.

Hypersensitivity and Infusion Reactions

Site personnel will be aware of the risk of hypersensitivity reactions, which may present as infusion reactions, and monitor subjects closely. Subjects should remain under clinical supervision for 3 hours after completion of the first 2 infusions. The infusion rate may be slowed or interrupted if the patient develops an infusion reaction. Should symptoms of acute hypersensitivity occur, an extended period of monitoring may be appropriate based on clinical judgment. This may include, but is not limited to, monitoring vital signs and observing any untoward reactions. Beyond the first 2 infusions, subjects should be monitored during infusion and for 30 minutes after infusion according to standard operating procedure for IV infusions. Infusion reactions occurred more frequently on the first two infusion days and tended to decrease with subsequent infusions. Delay in the onset of acute hypersensitivity reactions has been observed with recurrence of clinically significant reactions after initial resolution of symptoms following appropriate treatment. Therefore, subjects should be monitored during and for an appropriate period of time after administration of belimumab. Delayed-type, non-acute hypersensitivity reactions have also been observed and included symptoms such as rash, nausea, fatigue, myalgia, headache, and facial edema.

Serious infections

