7 REGULATORY AND REPORTING REQUIREMENTS

The entities providing oversight of safety and compliance with the protocol require reporting as outlined below. Please refer to Appendix G for definitions and Appendix H for a grid of reporting timelines.

Adverse events will be tracked from C1D1, as soon as the infusion of Belimumab, through 30 days following the last day of study treatment. All adverse events must be recorded on the toxicity tracking case report form (CRF) with the exception of:

- Baseline adverse events, which shall be recorded on the medical history CRF
- Adverse events that are less than CTCAE grade 3
- AEs not of special interest as defined in Section 7.1.4.1 (special interest AEs will be recorded regardless of grade, including those thought to be related to chronic GvHD)

Refer to the data submission schedule in Section 12 for instructions on the collection of AEs in the EDC.

Reporting requirements for Washington University study team may be found in Section 7.1.

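### Hy's Law liver events have no reporting class or clock of their own, so one not judged serious gets 60 days and may stay off the toxicity form

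*Combined protocol and SAP*

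**What the plan says.** Section 7.1.4 asks for reporting to the manufacturer of "all events of possible drug-induced liver injury with hyperbilirubinemia defined as" ALT at least 3x ULN with bilirubin at least 2x ULN (more than 35% direct), or ALT at least 3x ULN with INR above 1.5 where INR is measured. That sentence sets no deadline. It opens with "In addition to events described in Section 7.4 as reportable", but Section 7 contains only 7.1 and 7.2.

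Later in the same section the clock is 24 hours for SAEs and events of interest, and "within 60 days for any other reportable non-serious events". Section 7.1.4.1 then names four special-interest categories: serious hypersensitivity or infusion reactions, serious infections, malignancy, and suicidality. It says that the frequency "of the following Adverse Events of Special Interest will be assessed and included in the final report". Section 5.7 names the same four categories and says that serious events, including these, "must be reported to GSK within 24 hours of awareness".

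For recording, Section 7 lists exceptions to entry on the toxicity form. One is "Adverse events that are less than CTCAE grade 3". The next, a separate bullet, is events not of special interest, with a note that special-interest events are recorded whatever their grade. Section 12.1 carries these exceptions over to the Toxicity Form. Section 7.2 ends by saying that events not needing expedited reporting must still be in the EDC.

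**The concern.** The plan thought this event important enough to define by laboratory threshold, and no other event is made reportable that way. Yet it did not say which class the event belongs to, how fast it must be sent, or on which form it is entered. Each of those is then settled by default rules written for other events.

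The stake is the completeness of the safety data. The primary endpoint is safety and tolerability, from CTCAE-graded events between first dose and 30 days after the last (Section 8.1). A case that is neither serious nor of special interest can reach the manufacturer up to 60 days after awareness. It can also be absent from the form on which adverse events are collected, and it is not among the events whose frequency the final report must give. Section 5.7 does not list raised liver enzymes as expected with belimumab and points to acute GvHD as a possible cause. Attribution will therefore often be unclear, and a non-serious call is plausible.

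**Working it through.** The plan gives no figure to reproduce here. The check sets the rules side by side.

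1. **Does the event have its own clock?** No. Pregnancy, in the same section, has one (2 weeks), so deadlines could be set event by event; this one was left to the default.

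2. **Which default applies?**
   - Serious under Appendix G, through an outcome such as hospitalization or through the judgment-based important-medical-event criterion: 24 hours.
   - Special interest: 24 hours, but neither list has a liver item.
   - Otherwise: 60 days.

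   Appendix G does not make a Hy's Law event automatically serious. The FDA 7-day and 15-day rules for individual cases (7.1.3) also need a fatal, life-threatening or serious event. The missing Section 7.4 supplies no other route.

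3. **Must it be on the toxicity form?** The two Section 7 exceptions can be read in two ways, for an event that is not of special interest:

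| Reading of the exceptions | Below grade 3 | Grade 3 or above |
|---|---|---|
| Joint: exempt only if below grade 3 and not of special interest | may be left off | must be entered |
| Literal: each bullet exempts by itself | may be left off | may be left off |

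4. **Which grade would it have?** The documents do not print the CTCAE liver cut-offs. Assumption: ALT of 3 to 5x ULN and bilirubin of 2 to 3x ULN grade below 3. Events at the low end of the definition may then be left off under either reading. The definition has no upper limit, so higher values may reach grade 3 and must then be entered under the joint reading. If the assumption fails and every qualifying event is grade 3 or above, the joint reading leaves no gap and only the literal reading does.

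5. **Does Section 7.2 close the gap?** Its EDC sentence ends a list of four exceptions (planned hospitalizations, hospitalizations under 24 hours, respite care, events related to disease progression) and names no form. Section 7 sends EDC collection of adverse events to Section 12, and 12.1 reapplies the Section 7 exceptions. The provisions conflict, and Section 7.2 does not settle the conflict.

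6. **Size.** Planned enrolment is 10. If all are dosed, one unrecorded case is 1/10 = 10% of the safety population.

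**The case against.** The 60-day clause covers only non-serious events. An investigator may well judge a Hy's Law event to be an important medical event; it is then an SAE on the 24-hour clock, and if also an unexpected suspected reaction it enters the FDA 15-day route. This stands, and it limits the point to events not judged serious. A reader might infer that all Hy's Law events get 60 days; the text does not say so.

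The recording gap depends partly on CTCAE cut-offs that the documents do not show. This also stands for the joint reading, and is why the grade is stated as an assumption. The literal reading does not need it.

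ALT and total bilirubin are measured at every cycle and at +6 months (Sections 5.1.4.3, 10.1, 10.2), so the signal itself is not lost to the investigator. True, but a measured value is not a recorded adverse event, and the latter feeds the safety analysis.

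A reader might also infer that further doses would be given while the notice is pending. That does not follow. The clock governs notice to the manufacturer, while Section 5.4 leaves discontinuation for adverse events to the investigator's judgment. In any case, on nominal days 0, 14, 28, 56, 84, 112 and 140, a 60-day window after first exposure holds only 0 to 3 further doses (for example days 14, 28 and 56 after an event on day 1, and none after day 140).

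Finally, tiered clocks are a legitimate choice, and nothing in the documents requires a non-serious liver event to go within 24 hours. If 60 days is intended, the plan should say so; the recording conflict would remain.

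**Conclusion.** The point holds for Hy's Law events not judged serious. They are reportable, have no class or clock of their own, and default to 60 days. They may be left off the toxicity form if below grade 3, or at any grade on the literal reading of the third Section 7 exception, and Section 7.2 contradicts this without naming a form. That the toxicity form supplies the primary-endpoint data is an inference from Sections 7, 8.1 and 12.1, though a natural one. The size is one case in ten per omission; the documents give no expected rate of such events, so the chance of an omission cannot be stated. This is a cheap improvement to reporting and data capture, and it does not put the design in doubt.

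**What to change.** Add *possible drug-induced liver injury meeting the Section 7.1.4 definition* to the special-interest lists in 7.1.4.1 and 5.7. The event is then recorded at any grade, notified within 24 hours and counted in the final report. Ask for the suspected cause (liver GvHD, infection, drug) on the form.

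Reconcile Sections 7, 7.1.4, 7.2 and 12.1: state whether the grade and special-interest exceptions apply jointly or separately, and which form takes the events that Section 7.2 wants in the EDC. Replace the Section 7.4 reference with the intended one.

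The cost is one line in two lists, a clarified recording rule and a corrected reference. The downside is that some liver GvHD cases will generate a 24-hour notice.

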7.2 Exceptions to Expedited Reporting

Events that do not require expedited reporting as described in Section 7.1

- planned hospitalizations
- hospitalizations < 24 hours
- respite care
- events related to disease progression

Events that do not require expedited reporting must still be captured in the EDC.

8 MEASUREMENT OF EFFECT

8.1 Primary Endpoint: Safety and Tolerability

All subjects who receive any study treatment are evaluable for safety and tolerability. Subjects are followed for primary endpoint from first receiving study treatment until a 30-day follow-up after the last dose. Adverse events will be diagnosed and graded according to CTCAE v4.03 as described above.

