1.2.4 Pharmacokinetics and Drug Metabolism

Pharmacokinetic Parameter	Population Estimates (n = 563)
Peak concentration (C_{max} , mcg/mL)	313
Area under the curve (AUC, day · mcg/mL)	3,083
Distribution half-life ($t_{1/2}$, days)	1.75
Terminal half-life ($t_{1/2}$, days)	19.4
Systemic clearance (CL, mL/day)	215
Volume of distribution (Vss, L)	5.29

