3 PATIENT SELECTION AND ENROLLMENT

3.1 Inclusion Criteria

1. At least 18 years of age
2. ECOG performance status ≤ 2
3. Diagnosis of hematologic malignancy (i.e. acute myeloid leukemia, acute lymphoblastic leukemia, chronic lymphocytic leukemia, chronic myelogenous leukemia, Hodgkin's lymphoma, non-Hodgkin's lymphoma, myelodysplastic syndrome, chronic myelomonocytic leukemia)
4. Use of myeloablative or non-myeloablative conditioning regimen
5. Use of mobilized peripheral blood stem cells from fully HLA-matched related or unrelated donor as a graft source
6. Acute GvHD prophylaxis with methotrexate and tacrolimus
7. Documented complete remission and full donor engraftment (by STR identity testing) on Day +30 bone marrow biopsy
 - a. Complete remission: less than 5% blasts in an aspirate bone marrow sample with a count of at least 200 nucleated cells, no blasts with Auer rods or persistence of extramedullary disease PLUS absolute neutrophil count (ANC) $> 1,500/\mu\text{L}$, platelet count $\geq 50,000/\mu\text{L}$ and no leukemic blasts in the peripheral blood.
 - b. Negative minimal residual disease
 - c. Full donor engraftment by STR testing (either by bone marrow or peripheral blood testing)
8. Adequate end organ function:
 - a. Serum bilirubin $\leq 1.5 \times \text{ULN}$
 - b. Alanine aminotransferase (ALT) and aspartate aminotransferase (AST) $\leq 2.5 \times \text{ULN}$
 - c. Creatinine clearance $\geq 40 \text{ mL/min/1.73 m}^2$ by the Cockcroft-Gault formula
9. Women of childbearing potential must agree to use adequate contraception (hormonal or barrier method of birth control, abstinence) prior to study entry, for the duration of study participation, and for 16 weeks after the last dose of study drug. Should a woman become pregnant or suspect she is pregnant while participating in this study, she must inform her treating physician immediately.
10. Able to understand and willing to sign an IRB-approved written informed consent.

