5.9 Women of Childbearing Potential

Women of childbearing potential (defined as women with regular menses, women with amenorrhea, women with irregular cycles, women using a contraceptive method that precludes withdrawal bleeding, and women who have had a tubal ligation) are required to have a negative pregnancy test within 7 days prior to the first dose of belimumab.

Women of childbearing potential must agree to one of the following:

- Complete abstinence from intercourse from 2 weeks prior to administration of the first dose of belimumab until 16 weeks after the last dose of belimumab (if consistent with the preferred and usual lifestyle of the patient). Periodic abstinence (e.g., calendar, ovulation, symptothermal, post-ovulation methods) and withdrawal are not acceptable methods of contraception.
- Consistent and correct use of one of the following acceptable methods of birth control for one month prior to the start of the study agent, during the study, and 16 weeks after the last dose of study agent:
 - Oral contraceptive, either combined or progestogen alone
 - Injectable progestogen
 - Implants of levonorgestrel or etonogestrel
 - Estrogenic vaginal ring
 - Percutaneous contraceptive patches
 - Intrauterine device (IUD) or intrauterine system (IUS) with < 1% failure rate as stated in the product label
- Male partner sterilization (vasectomy with documentation of azoospermia) prior to the female subject's entry into the study, and this male is the sole partner for that subject. For this definition, "documented" refers to the outcome of the investigator's/designee's medical examination of the subject or review of the subject's medical history for study eligibility, as obtained via a verbal interview with the subject or from the subject's medical records.
- Double barrier method: condom and occlusive cap (diaphragm or cervical/vault caps) plus spermicidal agent (foam/gel/film/cream/suppository)

If a patient is suspected to be pregnant, belimumab should be immediately discontinued. In addition, a positive urine test must be confirmed by a serum pregnancy test. If it is confirmed that the patient is not pregnant, the patient may resume dosing. If a female

patient or female partner of a male patient becomes pregnant during therapy or within one month after the last dose of belimumab, the investigator must be notified in order to facilitate outcome follow-up.

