5.10 Study Stopping Rule

As this is a pilot study enrolling 10 eligible participants, the study will be suspended if any death considered at least possibly related to study treatment occurs during participation. The suspension may be lifted only if review of the event by the PI and QASMC results in a recommendation to permit further study enrollments.

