10 STUDY CALENDAR

10.1 Screening and Treatment Calendar

	Screening ¹	Baseline ²	C1	C2 +2wk	C3 +4wk	C4 +8wk	C5 +12wk	C6 +16wk	C7 +20wk
Informed consent	X								
H&P, ECOG PS	X		X	X	X	X	X	X	X
VS	X		X	X	X	X	X	X	X
CBC	X		X	X	X	X	X	X	X
CMP, LDH, phosphate, uric acid, magnesium	X		X	X	X	X	X	X	X
Pregnancy test ⁷	X		X ⁸	X	X	X	X	X	X
IgG and IgA		X							
Hepatitis serologies	X								
ECG (triplicate)	X		As clinically indicated						
Belimumab			X ⁵	X ⁵	X ⁵	X ⁶	X ⁶	X ⁶	X ⁶
Research blood		X ²			X ⁴				
Acute GvHD assessment		X			X	X	X	X	X
Chronic GvHD assessment					X	X	X	X	X
Immunosuppressive medication assessment	X	X	X	X	X	X	X	X	X
Medication reconciliation		Monthly							
AE assessment		X ----- X ⁹							

1. Screening assessments must take place between 30 and 80 days post-transplant
2. pre-treatment
3. Every 3 months starting at F/U #1 (+24wk)
4. Prior to treatment
5. Dosing window is +/- 3 days
6. Dosing window is +/- 1 week
7. Women of childbearing potential only
8. Pregnancy test need not be repeated on Cycle 1 if conducted within 7 days of Cycle 1 dose
9. AE assessment continues for 30 days post-EOT

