10.2 Follow-Up Calendar

Follow-up visits start 4 weeks after the end of protocol treatment (6-month follow-up is 6 months post-C1D1 and 4 weeks post-C7D1).

	+6mo	+9mo	+12mo	+15mo	+18mo	+21mo	+24 mo	+3 yr	+4 yr	+5 yr
CBC	X									
CMP, LDH, phosphate, uric acid, magnesium	X									
Pregnancy test ¹	X									
Research blood ²	X	X	X	X	X	X	X	X ²	X ²	X ²
Acute GVHD assessment	X									
Chronic GVHD assessment	X	X	X	X	X	X	X			
Immunosuppressive medication assessment	X	X	X	X	X	X	X			
AE assessment	X									

1. Women of childbearing potential only

2. Once there is evidence of B cell reconstitution, additional blood will be drawn (refer to Section 9), and will continue on an optional basis at 3, 4, and 5 years post-C1D1

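### Scheduled safety collection stops 30 days after the last dose, about 1.5 terminal half-lives, so later non-fatal serious and special-interest events are not solicited or counted, although their frequency is promised in the final report

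*Combined protocol and SAP*

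**What the plan says.** **Where collection ends.** Section 8.1 defines the primary-endpoint period: "Subjects are followed for primary endpoint from first receiving study treatment until a 30-day follow-up after the last dose". Section 7 tracks adverse events from the first infusion "through 30 days following the last day of study treatment". Special-interest events are exempt from the grade 3 threshold there but are given no longer period. The footnote to calendar 10.1 agrees: "AE assessment continues for 30 days post-EOT". In calendar 10.2 the only adverse-event mark is at +6 months, and the timing is explained as "6-month follow-up is 6 months post-C1D1 and 4 weeks post-C7D1". Visits then continue every 3 months to +24 months for chronic GvHD, immunosuppressive medication and research blood.

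**Where no end is stated.**
- Section 7.1.4 asks for serious and special-interest events to reach the manufacturer within 24 hours of awareness.
- Section 7.1.4.1 promises the frequency of four special-interest categories in the final report.
- Section 11 has serious toxicities monitored continually.
- Section 12 lists the Adverse Event Form as continuous.
- Section 12.1 gives a start for capture on the case report form but no stop, and refers to Section 7 for exceptions.

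**Other clocks after the last dose.**
- The pharmacokinetic table in Section 1.2.4 gives a "Terminal half-life" of 19.4 days.
- Section 5.6.2 requires five half-lives of wash-out after prior B-cell therapy, the point at which it regards the residual effect as minimal.
- Contraception continues "for 16 weeks after the last dose of study drug" (Section 3.1).
- Section 5.9 asks for notification if a patient, or a male patient's partner, "becomes pregnant during therapy or within one month after the last dose of belimumab", while Section 7.1.4 requires any pregnancy during study participation to be reported.

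**The concern.** The trial's main product is a safety description of 10 patients, meant to inform a phase II study. Section 1.2.3 accepts that the drug's mechanism could raise the risk of serious infection and malignancy. Neither is confined to the first month after an infusion, and malignancy in particular takes time to appear. Yet routine ascertainment stops while, on the protocol's own half-life, a substantial part of the terminal-phase concentration remains. The patients are still seen every 3 months, so the information is within reach and simply is not asked for.

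With 10 patients, one event moves an observed rate by 10 percentage points. A special-interest table that combines complete data to day 30 with whatever happens to be volunteered afterwards has no clear denominator. Because the sections disagree on the end date, study staff could also collect differently from one patient to the next.

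**Working it through.** **The plan's own safety figures (Section 13).** With N = 10 and a true rate of 20%, P(at least 1 serious event) = 1 − 0.80^10 = 0.893, stated as 90%. With a true rate of 5%, P(2 or more) = 0.086, stated as below 10%. Both reproduce. They take the event rate as given, so the choice of window does not alter them. The plan gives no figure that supports 30 days.

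**Half-lives elapsed.** Half-lives = days / 19.4. Fraction of terminal-phase concentration left = 0.5^(days / 19.4).

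| Time after last dose | Days | Half-lives | Left |
|---|---|---|---|
| +6-month visit (4 weeks after Cycle 7) | 28 | 1.44 | 36.8% |
| End of adverse-event window | 30 | 1.55 | 34.2% |
| Five half-lives (5 × 19.4; 13.9 weeks) | 97 | 5.00 | 3.1% |
| End of contraception period | 112 | 5.77 | 1.8% |
| +9-month visit, full course | 134 | 6.91 | 0.8% |

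These percentages describe terminal-phase decline only. They leave out the distribution phase (half-life 1.75 days in the same table), so they are not shares of the peak concentration.

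**Calendar.** Cycle 7 is at +20 weeks, day 140 from the first dose.
- Collection ends at day 140 + 30 = 170.
- Five half-lives end at day 140 + 97 = 237, so the present window covers 170/237 = 72% of that span. To 16 weeks it covers 170/252 = 67%.
- The +9-month visit is near day 274, and 274 − 140 = 134 days, about 19 weeks after Cycle 7. That is 134 − 97 = 37 days beyond five half-lives.
- A patient who stops after one dose has only about 30 days of collection but stays in follow-up under Sections 5.4 and 5.5.

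**Size of the gap, as an illustration.** The documents give no event rate for this population. I assume a constant hazard and a per-patient risk p over the planned 170 days. For a gap of g days, the chance that at least one of 10 patients has an event in the gap is 1 − (1 − p)^(10g/170). To five half-lives, g = 97 − 30 = 67. To 16 weeks, g = 112 − 30 = 82.

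| Assumed p over 170 days | g = 67 | g = 82 |
|---|---|---|
| 5% | 18% | 22% |
| 10% | 34% | 40% |
| 20% | 58% | 66% |
| 30% | 75% | 82% |

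A falling hazard would lower these figures and a rising one would raise them.

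**The case against.** The best defence is that treatment plus 30 days is a clearly stated window. In a descriptive single-arm study it defines the endpoint and does not distort it. That stands: a reader might infer that the primary endpoint is biased towards safety, but no comparison or test depends on it, and the fix leaves it unchanged.

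Four other strong readings are tempting and also fail.

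- *The plan treats exposure as lasting 16 weeks.* It does not say so. The 16 weeks is a contraception requirement only, and Section 5.9 uses one month for pregnancy notification. The case here rests on the stated half-life. Section 5.6.2 offers an analogy, but its rule concerns earlier B-cell therapy.
- *Late events are simply missed.* The undated routes in Sections 7.1.4, 11, 12 and 12.1 would catch some of them. Section 5.5 follows patients removed for unacceptable adverse events until resolution or stabilization, and deaths and relapse have their own forms. What is lacking is systematic solicitation and counting.
- *Late treatment-related deaths could not be judged.* The stopping rule concerns "any death considered at least possibly related to study treatment occurs during participation". Section 12.1 requires a death due to an adverse event to be recorded as grade 5 under that event and on the Death Form, and Section 5.10 sends the event for review. The rule can work without routine adverse-event visits.
- *B-cell recovery at 18 to 24 months shows a lasting drug effect.* Section 9 anticipates that timing after transplant without attributing it to belimumab, and Section 1.1.2 links delayed recovery to chronic GvHD itself.

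One objection stands as a cost. Later events are harder to attribute after transplant and GvHD treatment. Section 5.1.2 stops general medication recording 30 days after the last dose, and the control outcomes listed in Section 8.3 do not include infections or adverse events.

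**Conclusion.** The point holds in a limited form. Scheduled collection and the primary endpoint end at 1.55 terminal half-lives, with about 34% of terminal-phase concentration left, against 97 days for five half-lives. Beyond that point, non-fatal serious infection, malignancy and suicidality are neither sought nor counted in a planned way, although Section 7.1.4.1 promises their frequency and several sections set no end date.

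The half-life figures rest only on the protocol's table, which is not specific to transplant recipients. The illustrative 18% to 82% chance of at least one event in the gap rests on an assumed constant hazard and assumed risks, and should be read as a range only. The primary endpoint remains usable as defined. This is an inexpensive improvement together with an inconsistency to resolve, and the study's conclusions do not otherwise depend on it.

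**What to change.** 1. Keep 30 days for the primary endpoint and for general adverse events.
2. Add solicited collection of serious and special-interest events at the +9-month visit. For patients who stop early, use the first scheduled visit at least five half-lives (97 days) after the last dose.
3. Record malignancy on the existing Follow-Up Form to 24 months.
4. Report the 30-day and extended-window counts side by side, with each patient's follow-up time, because the extended period will differ between patients.
5. Reconcile Sections 7, 8.1, 10.1 and 10.2 with Sections 7.1.4, 7.1.4.1, 12 and 12.1, so that each type of event has one stated end date.
6. Reconcile the one-month pregnancy notification in Section 5.9 with reporting throughout study participation in Section 7.1.4, and with the 16-week contraception period in Sections 3.1 and 5.9.

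**Cost.** Calendar marks and a few form entries for 10 patients, with no added visits and no change in sample size. Later events will be less certainly attributable. To support attribution, general medication recording would have to continue to the same visit, which is a modest extra burden.
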